8.1. Retrospective Data

Data collected in the clinical routine, e.g. demographics, medication intake, concomitant diseases and procedures, disease and motor severity, detailed neuropsychological assessments, and detailed non-motor symptom assessments, will be included in the data analysis. If these parameters are collected when participating in other clinical studies, these will also be included.

8.2. Neuropsychological testing

The aim is to diagnose PD-MCI and PDD according to the Level-II recommendations of the Movement Disorder Task Force [9, 10, 12]. Therefore the following five domains will be quantitatively assessed using the Consortium to Establish A Registry of Alzheimer' Disease (CERAD-Plus) battery, three subtests of the Wechsler Intelligence Tests for Adults (WIE), and one subtest of the Leistungsprüfsystem für 50- bis 90-Jährige (LPS50+). At least two tests are assigned to each cognitive domain:

- Executive functions: Lexical and phonemic fluency (CERAD-Plus), Trail Making Test Part B
- Attention/working memory: Digit-Symbol Test (WIE), Letter-Number Sequencing (WIE)
- Language: Boston Naming Test (CERAD-Plus), Similarities (WIE)
- Memory: Word List learning, recall, and discriminability (CERAD-Plus) and Praxis recall (CERAD-Plus)
- Visuospatial abilities: Praxis (CERAD-Plus), Fragmented Words (LPS-50+)

The MMSE included in the CERAD-Plus, as well as the Montreal Cognitive Assessment will serve as global cognitive screening scales.

8.4. Home-based movement assessment (Accelerometer)

Physical activity directly influences health-related quality of life in PD [28], with specific aspects of physical activity decreasing with the severity of cognitive impairment [29]. We will therefore conduct a home-based movement assessment in a random subgroup of patients, to examine the influence of physical activity on cognition and other non-motor symptoms in PD. Participants will be asked to wear an accelerometer (MoveMonitor, McRoberts, The Netherlands) on their lower back for 7 consecutive days in their home environment. The accelerometer is capable of data uptake for 7-10 days, and assesses various movement parameters (e.g. time spent sitting, lying, walking, and standing, as well as step count).

8.5. Caregiver ADL assessments

Caregiver assessments have a crucial role determining a diagnosis of PDD, by examining whether patients are able to care for themselves and carry out their daily activities. The Bayer Activities of Daily Living (Bayer ADL) scale consists of 25 questions answered by the caregiver that evaluate the patient's ability to perform activities of daily living. The Informant Questionnaire on Cognitive Decline in the Elderly (IQ-CODE), a brief screening tool of dementia, compares patients' current abilities to how they were two years ago. This provides a useful marker for cognitive ADL progression, as well as helps to distinguish cognitive decline from normal aging. The caregiver assessment of ADL using the FAQ allows us to compare patient and caregivers' evaluation of ADL impairments.

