3.1. Background

Presence and severity of non-motor symptoms modulates the rate of Parkinson's Disease (PD) progression with a high impact on patients' quality of life [1-3]. One major clinical milestone in the course of the disease is the conversion to Parkinson's disease dementia (PDD), dramatically increasing the risk for nursing home placement and mortality [4]. One of the greatest risk factors for PDD is the development of mild cognitive impairment in PD (PD-MCI) [5]. However, only a subgroup (26% to 39.1%) of patients with PD-MCI have been reported to convert to dementia, while others present with a stable cognitive status or revert to normal cognitive function [6-8]. For an early and effective treatment, the identification of a high-risk group for PDD among those with PD-MCI is essential.

The core feature that differentiates PDD from PD-MCI is the loss of the ability to perform activities that are necessary for independent living [9, 10], emphasizing the importance of valid and reliable activities of daily living (ADL) assessments in PD [11]. To confirm the diagnosis of PDD, ADL disabilities should be primarily caused by cognitive, not motor, dysfunction [10, 12]. As PD is primarily a movement disorder, the distinction between motor and non-motor contributions to ADL in PD is an obvious challenge [13].

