4.1. Hypothesis and research questions

Based on previous reports and preliminary results, we hypothesize that PD-MCI patients with a more pronounced cognitive-driven ADL impairment (FAQ_{Q>1}) are at higher risk for conversion to PDD than PD-MCI patients with ADL impairment primarily related to motor function (FAQ_{Q≤1}).

1. Stratification of subgroups according to their baseline cognitive status (PD-MCI vs. normal cognition, PD-CN) and ADL function (cognitive-driven (FAQ_{Q>1}) vs. motor-driven (FAQ_{Q≤1})).
2. Defining progression of ADL impairment over time.
Aim 2.1: Evaluation of stability and/or progression of ADL status between baseline and follow-up (FAQ_{Q>1} vs. FAQ_{Q≤1}).
3. Evaluation of the interaction between cognition and ADL function over time.
Aim 3.1: Evaluation of conversion rates to PD-MCI and PDD according to baseline ADL status (FAQ_{Q>1} vs. FAQ_{Q≤1}).
Aim 3.2: Prediction of PD-MCI (among PD-CN) and PDD according to baseline ADL, cognitive, genetic, and biomarker profiles in blood and CSF.
Aim 3.3: Progression of decline in cognition and ADL function in relation to Amyloid and Tau burden.

5. Study duration

Total duration of the study is 2 ½ years.

6. Study population

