REM Sleep behavior questionnaire (RBDS-Q)	2 min
Apathy Evaluation Scale (AES)	3 min
Questionnaire for Impulsive-Compulsive Disorders in Parkinson's Disease-Short (QUIP-Kurz)	3 min
Unified Parkinson's Disease Rating Scale (UPDRS) Parts I-II	6 min
International Consultation on Incontinence Questionnaire-Short Form (ICIQ-SF)	2 min
Patient Perception of Bladder Condition (PPBC)	1 min
Top-10 Priority List	5 min
Saarbrücker Persönlichkeitsfragebogen (SPF)/ Interpersonal Reactivity Index (IRI)	5 min
Total time of clinical assessment:	185 min
Optional Home-based movement assessment (Accelerometer)	7 days

For this scientific study, all investigations will be performed in an ambulatory setting and need the study participants to be available for at least 3 hours and 5 minutes, not including the optional blood marker sampling (blood: 15 min, CSF: 30 min). To evaluate the association between the onset and severity of both motor and non-motor symptoms which might indicate disease progression and are therefore more pronounced in PD patients with mild ADL dysfunction, a comprehensive clinical assessment will be conducted.

- If patients agree to the optional CSF and/or blood collection (see also 8.6):
 - Blood collection 15 min
 - CSF 30 min**Total time for biomarker sampling:** 45 min

Caregiver assessments:

To validate the patient's self-impression, the following caregiver questionnaires and interview scales will be applied, needing caregivers to be available for at least 40 minutes. Caregiver assessments will only be performed if the respective patient has agreed to the interview.

Table 2: Overview of caregiver assessments

Assessment	Time
Explanation of the study requirements	10 min
Interview-based ratings:	
Informant Questionnaire on Cognitive Decline in the Elderly (IQ-CODE)	6 min
Tübinger Activity of Daily Living Inventory for Parkinson's disease	6 min
Questionnaires:	
Pfeffer Functional Activities Questionnaire (FAQ)	4 min
Bayer Activities of Daily Living Scale (Bayer ADL)	5 min
Top-10 Priority List	5 min
Saarbrücker Persönlichkeitsfragebogen (SPF)/ Interpersonal Reactivity Index (IRI)	4 min
Total Time of caregiver assessment:	40 min

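### Nothing keeps the FAQ, or knowledge of the baseline FAQ_Q group, out of the PDD diagnosis, so the outcome could partly draw on the predictor

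*Combined protocol and SAP*

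**What the plan says.** **Exposure.** Section 4.1 hypothesises that "PD-MCI patients with a more pronounced cognitive-driven ADL impairment (FAQ_{Q>1}) are at higher risk for conversion to PDD" than PD-MCI patients with FAQ_Q≤1. Section 3.2 defines FAQ_Q as (FAQ_C + 1)/(FAQ_M + 1) and reads a value above 1 as ADL impairment that is more cognitive than motor.

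**Outcome.** Section 3.1 states: "The core feature that differentiates PDD from PD-MCI is the loss of the ability to perform activities that are necessary for independent living". It adds: "To confirm the diagnosis of PDD, ADL disabilities should be primarily caused by cognitive, not motor, dysfunction". Section 8.2 says "The aim is to diagnose PD-MCI and PDD according to the Level-II recommendations of the Movement Disorder Task Force" and assigns tests to five cognitive domains. It names no ADL instrument, cut-off or decision rule for the functional part of the diagnosis.

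**Instruments at follow-up.** Section 8.5 opens with "Caregiver assessments have a crucial role determining a diagnosis of PDD" and then describes the Bayer ADL, the IQ-CODE and the caregiver FAQ. For the last it gives one purpose: "The caregiver assessment of ADL using the FAQ allows us to compare patient and caregivers' evaluation of ADL impairments". Table 1 also lists the patient FAQ. Section 8, before Table 2, says: "Caregiver assessments will only be performed if the respective patient has agreed to the interview".

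**Masking.** Section 10.1.1 describes pseudonymised data entry. No section describes masking of the diagnosing rater to the FAQ or to the baseline group, or independent adjudication.

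**Analysis.** Section 7 plans relative risks of conversion by baseline group.

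**The concern.** The property that turns PD-MCI into PDD, cognitively caused ADL loss, is the property FAQ_Q is built to capture, and the same questionnaire is collected again when the diagnosis is made. Two routes are left open:

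- **Instrument.** If follow-up FAQ answers feed the functional criterion, part of the outcome is measured with the tool that defined the exposure (incorporation bias).
- **Rater knowledge.** FAQ_Q was developed on baseline data from the ABC-PD cohort that is now being followed up. A rater who knows the baseline group may read a borderline case accordingly (diagnostic-review bias).

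A related gap is that caregiver information is called crucial but depends on the patient's agreement, and no rule covers a diagnosis made without it.

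Section 4 wants the result to pick out high-risk PD-MCI patients for future trials. If either route operates, a positive relative risk cannot be told apart from an artefact, and later modelling cannot recover the difference.

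**Working it through.** **1. The plan's own figures.** Follow-up sample (section 6.3): 262 × (1 − 0.20) = 209.6, stated as 209. Expected PDD cases (section 7): 209 × 0.13 = 27.2 and 209 × 0.28 = 58.5, stated as 27 to 58. Both reproduce.

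**2. Size of the main comparison.** PD-MCI share 43% (section 6.1): 0.43 × 209 = 89.9, about 90. Share with FAQ_Q>1, 32.6% (section 3.2): 0.326 × 90 = 29.3, so about 29 against 61. This assumes that dropout is unrelated to group and that the preliminary split carries over.

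**3. What this comparison can detect.** The setting is 80% power, two-sided 5% (assumed, as the plan gives no alpha), with the normal approximation for two proportions. Section 3.1 reports conversion of 26% to 39.1% in PD-MCI. If 26% of the FAQ_Q≤1 group convert, about 56% must convert in the other group (RR 0.563/0.26 = 2.2). If 39.1% convert, about 70% must (RR 0.701/0.391 = 1.8).

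**4. Effect of a few false labels.** Let true conversion p be equal in both groups, and let a fraction f of the FAQ_Q>1 non-converters be wrongly labelled PDD. The values of f are assumptions.

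- Observed risk with FAQ_Q>1: p + (1 − p)f. Apparent RR: [p + (1 − p)f]/p.
- Extra labels: 29 × (1 − p) × f.
- Rejection rate: Φ[(d − 1.96·SE0)/SE1] + Φ[(−d − 1.96·SE0)/SE1], where d is the risk difference, SE0 the pooled and SE1 the unpooled standard error.

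For p = 0.26 and f = 0.20:
- Observed risk 0.26 + 0.74 × 0.20 = 0.408; RR 0.408/0.26 = 1.57.
- Extra labels 29 × 0.74 × 0.20 = 4.3.
- d = 0.148, SE0 = 0.104, SE1 = 0.107; rejection about 30%.

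| p | f | extra labels | apparent RR | rejection (nominal 5%) |
|---|---|---|---|---|
| 26% | 5% | 1.1 | 1.14 | 7% |
| 26% | 10% | 2.1 | 1.28 | 12% |
| 26% | 20% | 4.3 | 1.57 | 30% |
| 26% | 30% | 6.4 | 1.85 | 55% |
| 39.1% | 10% | 1.8 | 1.16 | 9% |
| 39.1% | 20% | 3.5 | 1.31 | 19% |
| 39.1% | 30% | 5.3 | 1.47 | 37% |

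Only the difference in error between groups matters. With p = 26% and errors of 20% against 5%, the RR is 0.408/0.297 = 1.37 and rejection is 19%. Equal error rates give RR 1.

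**5. Direction of a reporting-style effect.** Section 3.2 puts five items in FAQ_C and seven in FAQ_M, each scored 0 to 3 and divided by 3.

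- Every item scored 1: (5/3 + 1)/(7/3 + 1) = 0.80.
- Every item scored 2: (10/3 + 1)/(14/3 + 1) = 0.76.
- Every item scored 3: (5 + 1)/(7 + 1) = 0.75.
- Every item scored 0: 1/1 = 1.
- Items 1, 2 and 9 scored 1, the rest 0: (1 + 1)/(0 + 1) = 2.

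Uniform over-reporting falls in the FAQ_Q≤1 group. Only a style specific to the cognitive items leads to FAQ_Q>1.

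**The case against.** The documents never make the FAQ a diagnostic input. Section 8.5 gives each caregiver tool its own purpose, and for the FAQ that purpose is comparing patient and caregiver views. Repeating the patient FAQ is explained by Aim 2.1, the stability of ADL status over time. Exposure and outcome lie about 46.6 months apart, and PDD also requires deficits on a separate cognitive battery. Uneven caregiver input is inferred from a consent condition: section 10.3 says a caregiver will be contacted, and no coverage rate is given. Whether the cited diagnostic criteria already settle the ADL decision cannot be checked from these documents.

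Most of this stands, and it rules out three stronger readings that a reader might infer:

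- **That the outcome is circular.** The documents show an open route, not its use.
- **That a stable reporting style would favour the hypothesis.** Because FAQ_Q is a ratio, the sign of such an effect is undetermined (step 5).
- **That the artefact amounts to an RR of about 1.3 to 2.5.** That range comes from a bivariate normal model with assumed correlations of 0.3 to 0.7 between baseline score and follow-up criterion, and 50% or 65% of patients meeting the criterion. It is a worst case. It lets the FAQ alone set the criterion, treats the ratio and the criterion as one score, and counts all persistence as artefact, although persistence of real early impairment is the hypothesis itself. At a correlation of 0.1 the RR is only about 1.1.

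The objection does not close the gap. A stated comparison purpose does not exclude diagnostic use when the section opens by giving caregiver assessments as a group a crucial diagnostic role. Nor does the time gap stop a rater from knowing the baseline group.

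**Conclusion.** The concern holds as a risk. The plan neither names the ADL basis of the PDD diagnosis nor separates it from the FAQ and the baseline FAQ_Q group. The outcome could therefore partly draw on the predictor's instrument or on knowledge of exposure. The documents do not show that it does, and the size is unknown.

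Bias from a rater who knows the baseline group would be expected to favour the hypothesis; for reporting style no direction can be given. With about 29 against 61 patients the comparison is sensitive to a few labels: about 4 false PDD diagnoses confined to the FAQ_Q>1 group give an apparent RR of about 1.6 at 26% true conversion, or about 1.3 at 39.1%. These values rest on the assumed 20% error rate, on equal true conversion and on the group sizes in step 2. The change should be made, because it is cheap and the problem cannot be repaired after the diagnoses are recorded.

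**What to change.** - State in sections 8.2 and 8.5 that neither the patient nor the caregiver FAQ enters the PDD decision.
- State that the functional criterion is judged from other ADL tools already collected, with the investigators specifying which and how. Tables 1 and 2 include the Pill-Questionnaire, the Bayer ADL, the IQ-CODE and the Tübinger ADL inventory. The documents do not support choosing one of them here as the common basis.
- Record the diagnosis in REDCap before the rater can see baseline FAQ or FAQ_Q data.
- In section 7, add a repeat of the main relative risk with and without patients who lack caregiver information.

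The cost is protocol wording, a database access step and one sensitivity analysis. No new instrument or visit is needed. The real loss is the FAQ as supporting diagnostic information. If the investigators never meant to use it that way, the first item costs one sentence.

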8.6. Biomaterial collection

8.6.1. CSF and blood collection

Blood collection: Serum (about 89 ml) will be collected for routine analyses in the Zentrallabor and the Neurochemisches Labor of the Universitätsklinikum Tübingen (UKT), for targeted biomarker search, for explorative proteomic and metabolomics approaches, as well as for the determination of genetic markers (APOE Genotype, MAPT, COMT, and GBA). This amount does not represent any health hazard. Blood samples will be collected in the morning, on an empty stomach.

Through venipuncture, the following samples will be taken for analysis and will remain in the Hertie Institut für klinische Hirnforschung (Ethic Proposal: 199/2011BO1):

- 10 ml venous blood for the determination of routine values in the Zentrallabor (1 Serum tube)
- 3 ml of venous blood (1 PaxGene tube) for RNA Isolation
- 20 ml of venous blood in 2 large EDTA tubes
- 10 ml of venous blood in 1 Serum tube

CSF collection: The lumbar puncture at level L3/L4 or L4/L5 of the spine will be performed by a qualified clinician. The applicants have extensive experience with this procedure (see e.g. Ethical proposals 46/2010 and 404/2010). Subjects will be closely monitored during and after the procedure. Up to 15 ml of CSF will be collected unless there is evidence of clinically significant coagulopathy or thrombocytopenia that would interfere with the safe conduct of the procedure. This amount does not represent any health hazard. The first 2 ml of CSF will be processed at the Zentrallabor to conduct standard analyses on cell count, protein, and glucose levels, while another aliquot will be sent to the Neurochemisches Labor to conduct analyses of neurodegenerative markers such as Abeta1-42 and Abeta1-40.

8.6.2. Tissue collection

Not applicable.

8.6.3. Analysis of biomaterial

A structured and integrated exploration of biomaterial in combination with the analysis of the extensive quantitative dataset obtained in this study bears the chance for a better molecular,

biochemical, and eventually functional understanding of one of the most debilitating symptoms associated with PD, i.e. cognitive deterioration.

For all patients, DNA, CSF, and plasma were sampled at baseline. Using the NeuroChip, patients were screened for genetic variants associated with dementia and PD. CSF levels of A β 1-42, phosphor- and total Tau were determined within the frame of the ABC-PD study.

In collaboration with the company ADX, represented by [name] and [name], the following baseline CSF biomarkers were provided for further analysis of 200 patients: A β 1-42, A β 1-40, A β 1-38, phosphor Tau 181, NF heavy, neurogranin, BASE-1, and alpha-synuclein. Thus, biomaterial will be primarily analysed locally, but will also be shared with non-profit research organisation partners such as ADX.

At time of follow-up, a maximum of 100 PD patients are expected to give a second CSF sampling. Levels of CSF biomarkers indicating cognitive worsening [30-35] will be measured using the solid phase enzyme essays from Fujirebio Germany GmbH: A β 1-42, A β 1-40, phosphor- and total Tau.

8.6.4. Storage of biomaterial

All samples will be stored at -80°C until use. To maximize confidentiality, all biomarker samples and information associated with the samples will be coded to prevent the exposure of the subject's information and identity. This coding process allows location and destruction of a sample at the subject's request. In addition, sample information is stored in one secured electronic database, while biomarker data is stored in an independently secured database on a different computer. No one except the investigators of the UKT will have access to the database to deduce the identity of the patient.

9. Risks and possible adverse reactions, end of the study

9.1. Neuropsychological testing

No relevant risks.

9.2. Comprehensive non-motor symptom assessment and Top-10 Priority List

No relevant risks.

9.3. Home-based movement assessment (Accelerometer)

No relevant risks.

9.4. Caregiver ADL Assessments

No relevant risks.

9.5. Biomaterial (Blood and CSF) collection

Venipuncture is usually well tolerated and is rarely associated with complications. However, at the site of injection it may cause symptoms such as bruising, small scars, induration, abnormal sensations around the puncture due to unintentional nerve injury (median nerve in

some cases with long-lasting sensory and motor deficits), infection, phlebitis (thrombophlebitis), a thrombosis, or it can wash away the smallest blood clots (embolisms). Circulatory reactions (so-called vagovasal reactions) can also occur. However, complications of this kind have rarely occurred so far.

Lumbar puncture is a routine assessment in neurological hospitals. The risk of injury of nerves, bones or other viscera is possible in theory but is extremely unlikely because of atraumatic injection needles. The needle prick can hurt locally and, in 10 percent of cases, radiating in the legs due to touching one of the lumbar nerve roots may occur for the fraction of a second. In theory, a local hemorrhage or an infection is possible. However, this has never occurred during the thousands of lumbar punctures performed every year at the Neurology Department of the UKT in the context of diagnostic measures ever since atraumatic needles have been available. During a period of hours to days, headaches can occur in an upright position. In very rare cases, it can cause patients to become bedridden for several days, a clear indication for a blood patch. A blood patch is another “lumbar puncture” at the place where the first puncture was performed, without collection of CSF but this time injecting autologous blood into the tissue *without penetrating* the dura mater again. It is hypothesized that this procedure closes the hole leading to CSF leakage. Ever since the introduction of atraumatic needles, the frequency of post-puncture headache in people older than 50 years has decreased substantially and is now below 2% [36].

9.6. End of the study

December 2020.

10. Data protection

10.1. Data collection

Data collection and use of personally identifiable information for this study complies with the General Data Protection Regulation (EU) 2016/679. Participants will be given the appropriate information on dealing with data collected in the study and asked to sign a separate informed consent form concerning data protection.

10.1.1. Which data are collected; is it possible to identify the donor?

Data of every subject – name, age, disease duration, as well as all assessed parameters and results of the biomarker assessments – are collected in separate folders, and will be stored in a lockable office of the PI or his/her representative. As a database platform, the REDCap electronic data capture tool will be used [37]. The database will be secured with password protection, individually assigned to each team member with database access. Pseudo-anonymized data will be saved in the database inside the firewall of the medical faculty, using a 4-digit number not associated with any demographics of the study participant. Thus, the identification of a participant using only the code number is not possible and confidentiality will be ensured by use of these identification codes. The informatics manager and PI will only receive coded information that has been entered into the database under those identification numbers. Electronic communication with outside collaborators will involve only unidentifiable information.

